1.0 INTRODUCTION

1.1 Disease Background

Idiopathic Inflammatory Myopathy (IIM) or myositis is a heterogeneous group of disorders with an autoimmune pathogenesis characterized by muscle inflammation leading to muscle weakness. Many patients with IIM [primarily polymyositis (PM) and dermatomyositis (DM)] develop interstitial lung disease (ILD), a leading cause of morbidity and mortality in these patients. The prevalence of ILD varies in myositis, but in certain subsets (e.g. the antisynthetase syndrome), ILD can occur in up to 80-90% of patients and be the first and most prominent feature. ILD is the most common cause of mortality and morbidity in myositis. There are currently no approved treatments for myositis-associated ILD (Myositis-ILD) or anti-synthetase syndrome associated ILD (Syn-ILD). A T cell mediated pathogenesis has been posited for Myositis-ILD with bronchoalveolar lavage (BAL) showing activated T cells¹. There is strong biological plausibility for considering ABT in Myositis-ILD. In a mouse model of hypersensitivity pneumonitis (HP), characterized by activated T cells in the lung parenchyma (similar to Myositis-ILD), blockade of T cell co-stimulation by CTLA-4 Ig (CD28/B7 antagonist) ameliorated lung inflammation². Moreover, treatment with CTLA-4 Ig led to a significant decrease in lung damage and less inflammatory cells in the BAL fluid as well as a diminished CD4/CD8 T cell ratio³. CTLA-4 Ig ligands are present in autoinvasive CD8+ T cells in biopsies of PM-scleroderma patients⁴. CTLA-4 and CD28 are over-expressed on inflammatory cells and muscle cells in muscle biopsies of PM and DM patients^{4,5}. The goal of this proposal is to perform a collaborative multi-center trial among adult rheumatologists and pulmonologists to examine the efficacy and safety of ABT as a potentially important new therapeutic advance for Syn-ILD.

1.2 Abatacept Background and Rationale in IIM

ABT not only down-regulated T cells, thereby directly affecting lung and muscle inflammation in myositis, but also decreased the antigen-presenting capability of myocytes, inhibited macrophages and led to decreased pro-inflammatory cytokines (specifically IL-6, TNF alpha, and others), all of which are strongly implicated in the pathogenesis of myositis⁶. Moreover, CD80 and CD86 are expressed in antigen-presenting B lymphocytes and ABT decreases B lymphocyte expression, of importance in the pathogenesis of myositis and Myositis-ILD given the beneficial effects of rituximab for Myositis-ILD⁷⁻⁹. Anti-T cell therapy (e.g. tacrolimus and cyclosporine) has been shown by our investigative group and others to be effective in refractory patients with Myositis-ILD especially in those with the antisynthetase syndrome¹⁰⁻¹⁵. However, its use is limited by established toxicity, patient intolerance and the need for complex monitoring. Other case reports suggest that ABT has efficacy in treating the muscle and skin features of refractory PM and DM¹⁶⁻¹⁹, and the pathogenesis of Myositis-ILD is similar to that of muscle disease in myositis except that the target of inflammation and subsequent damage is different. There is encouraging evidence of the amelioration of Rheumatoid Arthritis (RA) associated ILD using ABT²⁰ as well as the lack of ILD worsening when RA is treated with ABT, a somewhat unique effect not shared with other biologics currently FDA-approved for RA. Given the rarity, heterogeneity and complexity of myositis and Myositis-ILD, any clinical study or trial is very difficult to perform and should only be done in specialized centers seeing such patients. Moreover, it is essential for clinical trials that myositis and ILD outcome measures be appropriately assessed.

1.2.1 Abatacept

ABT is a soluble fusion protein that consists of the extracellular domain of human cytotoxic T-lymphocyte-associated antigen 4 (CTLA-4) linked to the modified Fc (hinge, CH2, and CH3 domains) portion of human immunoglobulin G1 (IgG1). It is produced by recombinant DNA technology in a mammalian cell expression system. The apparent molecular weight of ABT is 92 kilodaltons. It is supplied as a sterile, white, preservative-free, lyophilized powder for parenteral administration. Following reconstitution with 10 mL of Sterile Water for Injection, USP, the solution of ABT is clear, colorless to pale yellow, with a pH range of 7.0 to 8.0. Each single-use vial of ORENCIA provides 250 mg ABT, 500 mg maltose, 17.2 mg monobasic sodium phosphate, and 14.6 mg sodium chloride for administration. The efficacy and safety of ABT was assessed in five randomized, double-blind, placebo-controlled studies in patients \geq age 18 with active RA diagnosed according to American College of Rheumatology (ACR) criteria.

Further information on ABA can be found in the Investigator's Brochure (IB).

1.3 Other Study Drug(s) Background

Not applicable

1.4 Study Rationale

There are currently no approved treatments for myositis-associated ILD (Myositis-ILD) or anti-synthetase syndrome associated ILD (Syn-ILD). A T cell mediated pathogenesis has been posited for Myositis-ILD with bronchoalveolar lavage (BAL) showing activated T cells¹. There is strong biological plausibility for considering ABT in Myositis-ILD. In a mouse model of hypersensitivity pneumonitis (HP), characterized by activated T cells in the lung parenchyma (similar to Myositis-ILD), blockade of T cell co-stimulation by CTLA-4 Ig (CD28/B7 antagonist) ameliorated lung inflammation². Moreover, treatment with CTLA-4 Ig led to a significant decrease in lung damage and less inflammatory cells in the BAL fluid as well as a diminished CD4/CD8 T cell ratio³. CTLA-4 Ig ligands are present in autoinvasive CD8+ T cells in biopsies of PM-scleroderma patients⁴. CTLA-4 and CD28 are over-expressed on inflammatory cells and muscle cells in muscle biopsies of PM and DM patients^{4,5}. The goal of this proposal is to perform a collaborative multi-center trial among adult rheumatologists and pulmonologist to examine the efficacy and safety of ABT as a potentially important new therapeutic advance for Syn-ILD.

2.0 OBJECTIVES

2.1 Primary

The primary objective is to evaluate the efficacy, safety and tolerability of ABT (125 mg SQ weekly) and standard of care (SOC) vs. SOC in patients with Syn-ILD in a multi-center, double-blind, randomized placebo-controlled proof of concept clinical trial.

Hypothesis: ABT will be efficacious, safe and tolerable in Syn-ILD patients.

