3.1.1 Study Schema

We will enroll 20 adult subjects with Syn-ILD across 5 clinical sites. We expect enrollment to be completed within 15 months. A 1:1 randomization scheme for active drug: placebo as a weekly SQ injection with their SOC for 24 weeks. All patients can then enter an optional open label follow-up after the 24-week randomized, controlled phase, during which all subjects receive 24 weeks of ABT in the same fashion as the initial study phase. This follow-up phase will assess durability, long term response and safety in patients who were in the active treatment arm while allowing the placebo arm to receive active drug, thus improving recruitment and study power.

Patient must have active ILD associated with anti-synthetase syndromes (a subset of myositis) that are being given SOC treatment for ILD. Patients could have refractory disease with flare up or new onset disease. Patient may or may not have active myositis (PM/DM). We anticipate the continued participation of all subjects in open label extension phase.

Open label phase: At the end of the active study period (week 24 closing visit), patients in either arm can enroll into the optional open-label phase of 24-week ABT therapy (125 mg SQ injection weekly).

a. **Standard of Care (SOC):** The SOC of patients with Syn-ILD includes steroids OR another IS agent OR a combination of steroid and another IS agent. Thus, we will allow steroids and/or only 1 additional IS agent. **Additional IS agent can be either mycophenolate mofetil (MMF) or azathioprine (AZA), but not both.** Patients on steroids alone can be enrolled without additional IS agent. Maximum dose allowed for MMF is 3 gms/day and for AZA is 200 mg/day. Patient should be on stable dose of MMF or AZA for 4 weeks and/or stable dose of steroids 2 weeks prior to Visit 1. Visit 1 is the time of first ABT/placebo dosing. Overall goal is to enroll patients into the trial as soon as the SOC drug has achieved stable dosing. Prednisone taper will be allowed at maximum dose of 60 mg at baseline (Visit 1), at which time a forced prednisone taper will commence as outlined below. Dose of concomitant medication cannot change throughout the phase I of the trial (24 weeks) unless safety/toxicity issues supervene.

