3.3.1 Primary Outcome Measures

The primary outcome criteria for efficacy will be the FVC% change from the baseline visit to week 24 between the 2 treatment arms (SOC/placebo vs. SOC/ABT). An intention to treat analysis will be used. Ranked ANCOVA will be used with average standardized rank change in the predicted FVC% as the outcome measure and the standardized rank baseline as a covariate. Primary outcome criteria for safety and tolerability will be adverse events (routine adverse events or tolerability issues and serious adverse event) between the 2 treatment arms (SOC/placebo vs. SOC/ABT). Chi-square (or Fischer exact test) and t-test (or Mann-Whitney) will be used based on data variable and distribution.

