3.3.3 Safety Outcome Measures

Safety is being assessed in one of the secondary endpoints listed above in Section 3.3.2. We will statistically compare the frequency of the following adverse events between the treatment and placebo arms.

Similarly, we will analyze the proportion of serious adverse events between the treatment and placebo arms. In addition, the number and percent of patients with AEs during the treatment period will be summarized.

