12.0 STATISTICAL CONSIDERATIONS

12.1 Determination of Sample Size

The sample size is 20 patients with 10 patients in each arm for a 24-week randomized double blind clinical trial. The sample size is justified based on this trial being a proof of concept pilot study. This study will allow us to determine an initial signal for possible efficacy of ABT in Myositis-ILD (Syn-ILD) as well as give safety and tolerability data. Moreover, it will allow us to determine an estimate of the effect size of the study drug and placebo to design a more definitive phase II/III clinical trial. In our cohort about 25% patients with SOC decline by FVC% of $\geq 15\%$ or death or

transplant. Assuming FVC decline by mean of 10% on SOC therapy and trial drug + SOC leads to improvement in FVC% (Even by mean of 5%) we will have >90% power to detect the difference with sample size proposed. Based on our database there is about 25% patients that decline FVC > 10% on SOC for myositis ILD.

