12.3 Methods of Analysis

Primary End Point:

The primary end point for statistical analysis will be the percent FVC changes from baseline to week 24 between the 2 treatments arms (SOC/placebo vs. SOC/ABT). Ranked ANCOVA, with average standardized rank change in the predicted FVC% as the outcome measure and the standardized rank baseline as a covariate will be used. Primary outcome criteria for safety and

tolerability will be adverse event (routine adverse events or tolerability issues and serious adverse event) between the 2 treatment arms (SOC/placebo vs. SOC/ABT). Chi-square (or Fischer exact test) and t-test (or Mann-Whitney) will be used based on data variable and distribution. Patients will be stratified for sub-analysis based on their SOC drug

Secondary Analysis (SOC/placebo vs. SOC/ABT) for Syn-ILD:

- a. Time to progression free survival where progression is defined as first occurrence of any of the following: death or lung transplant or $FVC \geq 10\%$ decline *or* $FVC \geq 5\%$ decline with $DLCO \geq 15\%$ decline. This will be done using Cox proportional hazards model and controlling for baseline demographics and $FCV\%$.
- b. Change in dyspnea, as measured by University of California San Diego Shortness of Breath Questionnaire (UCSD SOBQ) (range 0-120, higher score is worsening dyspnea), will be done using Mann-Whitney test.
- c. Time to improvement in $FVC\%$ by $\geq 10\%$. This will be done using Kaplan Meier survival curve and Cox's proportional hazards model after controlling for co-variates.
- d. Rates of death or requiring lung transplant using Chi-square (Fischer exact) test.
- e. Other individual PFT variables (FEV1%, DLCO%) similar to analysis done for primary outcome of $FVC\%$.
- f. Qualitative changes in HRCT chest over 6 months in the two arms using chi-square (or Fischer exact) test. Changes in semi-qualitative scoring of fibrosis over 6 months based on HRCT chest scan images collected from all sites and centrally read by an expert blinded radiologist, will be done as a separately and analyzed using analysis strategy similar to primary outcome.
- g. Steroid-sparing effect (calculated using prednisone dose equivalents) using paired t-test.
- h. Frequency of treatment failures: a) patient meeting worsening criteria or withdrawal due to worsening ILD anytime during the trial or b) $FVC\%$ worsening by 10% at 6 months, c) death or transplant within 6 months. Chi-square test will be used to compare between the two groups.

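### Safety is a primary outcome, but it is analysed only by tests of difference at 10 per arm; the plan gives no interval or criterion from which abatacept could be called safe and tolerable

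*Combined protocol and SAP*

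**What the plan says.** Section 2.1 puts safety and tolerability in the primary objective and adds the hypothesis that "ABT will be efficacious, safe and tolerable in Syn-ILD patients". Section 3.3.1 makes them a primary outcome: "Primary outcome criteria for safety and tolerability will be adverse events (routine adverse events or tolerability issues and serious adverse event", compared between arms. Sections 12.2.1 and 12.3 repeat this.

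The method in 3.3.1 and 12.3 is a choice of tests: "Chi-square (or Fischer exact test) and t-test (or Mann-Whitney) will be used based on data variable and distribution". Section 3.3.3 adds "We will statistically compare the frequency of the following adverse events between the treatment and placebo arms", does the same for the proportion of serious adverse events (SAEs), and then says that "the number and percent of patients with AEs during the treatment period will be summarized".

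On size, 12.1 states: "The sample size is 20 patients with 10 patients in each arm for a 24-week randomized double blind clinical trial". It justifies this by the trial being a proof-of-concept pilot, which will estimate an effect size for a later trial "as well as give safety and tolerability data". The only power statement, above 90%, concerns forced vital capacity (FVC).

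The plan gives no expected AE rate by arm, no significance level, no acceptable excess or margin, no confidence interval for any safety quantity, and no rule for reaching a conclusion of safe and tolerable.

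Section 3.3.3 also describes safety as covered by a secondary endpoint of 3.3.2. Section 3.3.2 lists no AE endpoint, and 3.3.1, 12.2.1 and 12.3 call safety primary. Section 3.3.3 refers to a list of adverse events that does not follow.

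**The concern.** The hypothesis and the method do not match. A test of difference can give evidence of harm. Failing to reject does not give evidence of no harm, unless the data also exclude an excess that would matter. The plan defines no such excess and plans no interval that would show what is excluded.

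With 10 per arm, a non-significant result is likely across a wide range of true excesses. The inferential output for a primary outcome would then look much the same for a drug with no added risk and for one that doubles or triples a 10% event rate. A report written to this plan could set a non-significant p-value beside the stated hypothesis, with nothing on the page to show how little that p-value says.

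**Working it through.** **Inputs.** 10 patients per arm (12.1), 1:1 allocation (3.1.1), and chi-square or Fisher's test for proportions (3.3.1, 12.3). Assumed because the documents give neither: two-sided alpha 0.05, and the event rates shown.

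**The plan's own figure.** There is no safety power to reproduce. For FVC, the assumed difference is 10 + 5 = 15 points. With power = Φ(15 / (SD·√(2/10)) − 1.96), SD = 10 gives Φ(3.35 − 1.96) = 92%, and 90% needs SD of at most 10.3 (9.8 with the t distribution). No SD is stated, so the figure can be neither confirmed nor refuted. It has no bearing on safety.

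**Smallest significant split, Fisher.**
- 5/10 versus 0/10: p = 2·C(10,5)/C(20,5) = 504/15,504 = 0.033.
- 4/10 versus 0/10: p = 2·C(10,4)/C(20,4) = 420/4,845 = 0.087.
- 6/10 versus 1/10: p = 2·(2,100 + 120)/77,520 = 0.057. With one placebo event, 7/10 is needed.

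**Exact power.** Sum Bin(a; 10, p_ABT)·Bin(b; 10, p_placebo) over all outcomes (a, b) with p ≤ 0.05. For 10% versus 30% with Fisher's test, the main terms are:
- b = 0: 0.3487 × P(a ≥ 5) = 0.3487 × 0.1503 = 0.0524
- b = 1: 0.3874 × P(a ≥ 7) = 0.3874 × 0.0106 = 0.0041
- b = 2: 0.1937 × P(a ≥ 8) = 0.1937 × 0.0016 = 0.0003

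The full sum is 0.057. The same enumeration gives:

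| Placebo vs abatacept | Fisher | Uncorrected chi-square |
|---|---|---|
| 5% vs 15% | 0.6% | 3.1% |
| 5% vs 25% | 4.8% | 14% |
| 10% vs 20% | 1.2% | 4.6% |
| 10% vs 30% | 5.7% | 14% |
| 10% vs 40% | 15% | 29% |
| 20% vs 40% | 5.8% | 13% |
| 20% vs 50% | 13% | 25% |
| 50% vs 80% | 13% | 25% |
| 10% vs 70% | 67% | 82% |

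For 80% power with Fisher's test, the abatacept rate would have to be about 70% against 5%, 77% against 10%, or 88% against 20%. Power of the t-test or Mann-Whitney for event counts was not calculated, because the documents give no distribution for them.

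**What the randomised phase can exclude** (two-sided exact 95% upper limits):
- 0/10: 1 − 0.025^(1/10) = 30.8%.
- 1/10: solve (1−p)^10 + 10p(1−p)^9 = 0.025, which gives p = 44.5%.
- 1/10 in each arm (p = 1.0): Wilson limits are 1.8% and 40.4%, so the Newcombe interval for the difference is ±√(0.082² + 0.304²) = ±32 points.

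**The case against.** The strongest reply is that this is a pilot and says so. Section 2.1 sets out to evaluate safety, 12.1 promises safety data and not proof, 3.3.3 plans a count-and-percent summary, and 11.2 commits to reporting all collected AEs in aggregate. Low power for AEs is unavoidable with 20 patients. Much of this stands. The sample size is not the fault, and a descriptive table is already planned. But that table carries no measure of uncertainty and sits beside the tests without replacing them. A pilot meant to inform a later trial needs estimates with intervals.

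A reader might infer that the sponsor will treat a non-significant comparison as showing safety. The documents do not support that: no section states the inference or a rule that leads to it. What can be said is that the plan does not say how the hypothesis would be judged and leaves that reading open.

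A reader might also infer that the tests have no useful power at all. That depends on the excess and on the test. Chi-square, which the plan names first, roughly doubles the Fisher power for several of the differences above, although its approximation is doubtful at such small counts. Very large excesses would often be seen (67% by Fisher for 10% versus 70%).

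Finally, the 31% and 45% limits describe the randomised phase only. If all 20 patients were exposed once the open-label phase is included, 0/20 would give an upper limit of 1 − 0.025^(1/20) = 17%. That phase is optional and uncontrolled, so it does not help the between-arm comparison.

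**Conclusion.** The concern holds in this form: a primary safety outcome, under a hypothesis that the drug is safe and tolerable, is analysed inferentially only by tests of difference that cannot support the hypothesis. There is no interval, margin or criterion to fill the gap. For increases of 10 to 30 points from placebo rates of 5% to 20%, power in the cases calculated is about 1% to 15% with Fisher's test and 3% to 29% with uncorrected chi-square. A non-significant result is therefore more likely than not throughout that range. These figures rest on an assumed two-sided 0.05 level and illustrative event rates. The exact upper limits of 31% and 45% need only the arm size and the 95% level. The weakness lies in the hypothesis wording and the choice of analysis; it is not a case for more patients.

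**What to change.** - **3.3.1, 3.3.3 and 12.3:** base the safety conclusion on estimation. Extend the number-and-percent summary in 3.3.3 to the proportion of patients with any AE, any SAE and any AE-related study-drug discontinuation, per arm with exact 95% confidence intervals. Add risk differences with 95% confidence intervals.
- Name the interval method for the risk difference in advance, because at this size it can disagree with the test: for 4/10 versus 0/10 the Newcombe interval is +4 to +69 points, while Fisher's p is 0.087.
- Treat any p-values as descriptive, and state that a non-significant comparison is not evidence of safety.
- **2.1:** reword the safety part of the hypothesis as an aim to estimate safety and tolerability.
- **3.3.3:** reconcile with 3.3.1, 12.2.1 and 12.3 on whether safety is primary or secondary, and supply or remove the list of adverse events it refers to.

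The cost is text changes and intervals on summary tables. Section 8.0 already has AEs, SAEs and AEs leading to interruption or discontinuation of study drug assessed at each visit, so no new data, visits or patients are needed. The downside is a more modest safety conclusion.

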2.2 Secondary

The secondary objectives include assessing: (a) radiographic improvement, (b) improvement in other PFT variables like FEV1 and DLCO, (c) time to improve in composite outcome for ILD by OMERACT, (d) death/transplant, (d) patient-reported outcomes of dyspnea, (e) rapidity and magnitude of response to ABT, (d) steroid-sparing effect of ABT, (e) durability of response, and (f) assessment of drug effect on other muscle or skin manifestations using standard myositis response criteria.

2.3 Exploratory

We plan to identify predictors of treatment response to ABT in Syn-ILD which will include the concomitant blood repository along with collection of clinical and demographic data collected during the course of the trial to study clinical, pathologic and immunologic factors associated with a response or lack of response to the study drug. This objective will be achieved in the future using a separate study after the completion of the clinical trial, but the samples will be collected as part of the current trial.

3.0 STUDY DESIGN

3.1 Description of the Study

This is a proof of concept study to evaluate the efficacy, safety and tolerability of ABT in Syn-ILD in a multi-center randomized, placebo-controlled 6-month (24-week) pilot study followed by a 24 week open label extension phase.

3.1.1 Study Schema

We will enroll 20 adult subjects with Syn-ILD across 5 clinical sites. We expect enrollment to be completed within 15 months. A 1:1 randomization scheme for active drug: placebo as a weekly SQ injection with their SOC for 24 weeks. All patients can then enter an optional open label follow-up after the 24-week randomized, controlled phase, during which all subjects receive 24 weeks of ABT in the same fashion as the initial study phase. This follow-up phase will assess durability, long term response and safety in patients who were in the active treatment arm while allowing the placebo arm to receive active drug, thus improving recruitment and study power.

Patient must have active ILD associated with anti-synthetase syndromes (a subset of myositis) that are being given SOC treatment for ILD. Patients could have refractory disease with flare up or new onset disease. Patient may or may not have active myositis (PM/DM). We anticipate the continued participation of all subjects in open label extension phase.

Open label phase: At the end of the active study period (week 24 closing visit), patients in either arm can enroll into the optional open-label phase of 24-week ABT therapy (125 mg SQ injection weekly).

a. **Standard of Care (SOC):** The SOC of patients with Syn-ILD includes steroids OR another IS agent OR a combination of steroid and another IS agent. Thus, we will allow steroids and/or only 1 additional IS agent. **Additional IS agent can be either mycophenolate mofetil (MMF) or azathioprine (AZA), but not both.** Patients on steroids alone can be enrolled without additional IS agent. Maximum dose allowed for MMF is 3 gms/day and for AZA is 200 mg/day. Patient should be on stable dose of MMF or AZA for 4 weeks and/or stable dose of steroids 2 weeks prior to Visit 1. Visit 1 is the time of first ABT/placebo dosing. Overall goal is to enroll patients into the trial as soon as the SOC drug has achieved stable dosing. Prednisone taper will be allowed at maximum dose of 60 mg at baseline (Visit 1), at which time a forced prednisone taper will commence as outlined below. Dose of concomitant medication cannot change throughout the phase I of the trial (24 weeks) unless safety/toxicity issues supervene.

No other concomitant IS agent is allowed (e.g. IVIG, plasmapharesis, rituximab, methotrexate, tacrolimus, cyclosporine, other biologics. Hydroxychloroquine and pirenade **are permitted** during the trial if on a stable dose for 4 weeks prior to trial entry.

Forced steroid taper (Prednisone or other steroid in prednisone equivalent doses) in subject on a stable dose of steroid 2 weeks prior to visit 1.

a. **Steroid Tapering:** May begin within or at 1 week after beginning study drug. Goal is to taper steroid to 5 mg or lower dose within 8 weeks. Recommended daily prednisone taper (or other forms of steroid in equivalent doses)

- i. 60 mg decreased to 40 mg after 1 week
- ii. 40 mg decreased to 30 mg after 1 week
- iii. 30 mg decreased to 20 mg after 1 week
- iv. 20 mg decreased to 15 mg after 1 week
- v. 15 mg decreased to 10 mg after 1 week
- vi. 10 mg decreased to 7.5 mg after 1 week
- vii. 7.5 mg decreased to 5 mg after 1 week
- viii. Further decrease as per treating physician.

b. **Steroid at Entry:** Maximum steroid dose allowed at study entry is ≤ 60 mg/day prednisone (or other forms of steroid in equivalent doses). If on a lower dose then the tapering scheme noted above should be employed based on the entry dose. Patients not on steroids are allowed in the study and are not allowed to start new steroids unless there is a disease flare.

c. **Steroid Dosing During Flare:** If in the clinical site investigator's opinion there are complications or worsening of disease that necessitate an increase in the prednisone dose (or other forms of steroid in equivalent doses) then the smallest reasonable increase should be considered (maximum increase of prednisone equivalent of 20 mg/day is allowed). After the increase, subjects should resume the prednisone taper noted above.

Concomitant medications will remain unchanged throughout Phase I, except changes made per the rescue medication protocol. During the open label Phase II, concomitant medications adjustments are permitted even if the subject has not met the definition of worsening.

Active ILD: Defined as (a) new onset of ILD (within 3 months of ILD diagnosis) or (b) worsening ILD as per the treating physician assessment necessitating a treatment change within last 3 months (with documented worsening of at least 2 of the 3 parameters: patient's report of worsening dyspnea, worsening in severity of ground glass opacities (GGO), reticulation or honeycombing or fibrosis on chest HRCT or a decline in the FVC% > 10% within last 6 months.)

Active Study Drug: A weekly dose of 125 mg SQ will be used in this 24-week trial and open label phase of 24 weeks.

Specimens (serum, cells etc.) collected and stored in a biospecimen repository at each study visit for future experimental studies. The repository will be located at the University of Pittsburgh, Division of Rheumatology. We will consider submission of ancillary proposals to conduct experiments designed to further elucidate biomarkers and basic physiologic and cellular mechanisms of disease resulting from Abatacept therapy.

Strategies for (1) allowing “rescue” therapies and (2) insuring that the original randomization treatment scheme is not revealed are discussed in Section 4.4.

Future Tests:

The Specimen Repository samples will be used in the future for two types of research: 1) immunologic and 2) genetic.

Immunology Research

Tests to be performed on the stored blood include the following: RNA-Seq analysis, autoantibody testing for the presence of myositis associated autoantibodies, serum interferon (IFN)-inducible chemokines, Th1, Th2, Th17, innate, and regulatory cytokines at baseline and later time points in this clinical trial to identify a biomarker signature predicting responsiveness to Abatacept. These immunology tests will be conducted in a research laboratory, not a public certified laboratory. Therefore, subjects will not be informed of these results.

Genetic Research

Genetic analysis. While the exact nature of the genetic research studies is not fully known, they may involve identifying genes that can: 1) increase the risk of developing autoimmune illnesses such as myositis, 2) modify the severity of autoimmune disease, or 3) control components of the immune system (immunogenetic studies).

